## 5 SAFETY ASSESSMENTS

Safety data will be summarized by treatment for the safety population unless otherwise indicated. [Table 7](#) summarizes the safety analyses to be carried out. AEs will be coded in accordance with the Medical Dictionary for Regulatory Activities (MedDRA). Severity of AEs will be graded by the investigator according to the NCI Common Terminology Criteria for Adverse Events (NCI-CTCAE) v4.03.

The treatment-emergent period is defined as the period from the date of the first dose of study treatment up to 30 days after the date of the last dose of study treatment or the day before initiation of subsequent anti-cancer therapy, whichever comes first.

The treatment-emergent adverse events (TEAEs) are those events that occur or worsen during the treatment-emergent period or that are related to the study treatment. TEAEs or deaths related to COVID-19 infection will be summarized or listed separately. All laboratory values will be converted to and reported as international standard (SI) units. In general, only data from the central laboratory will be summarized and analyzed. When central lab values are missing and local lab values are available, local lab values will be used. Laboratory parameters will be graded using the NCI CTCAE v4.03. Unless otherwise specified, only baseline and post-baseline values collected during the treatment-emergent period will be included in the safety analysis.

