1.3.2. Summary of Clinical Safety

In patients with NHL receiving rituximab monotherapy, NCI-CTC Grade 3 and 4 cytopenias were reported in 48% of patients. These included lymphopenia (40%), neutropenia (6%), leukopenia (4%), anemia (3%), and thrombocytopenia (2%). The median duration of lymphopenia was 14 days (range, 1-588 days) and of neutropenia was 13 days (range, 2-116 days). A single occurrence of transient aplastic anemia (pure red cell aplasia) and two occurrences of hemolytic anemia following rituximab therapy occurred during the single-arm studies. In studies of monotherapy, rituximab-induced B-cell depletion occurred in 70% to 80% of patients with NHL. Decreased IgM and IgG serum levels occurred in 14% of these patients ([Rituxan[®] USPI 2021](#)).

Specific safety considerations regarding the use of rituximab detailed in the rituximab regional prescribing information are described below ([MabThera[®] SmPC 2023](#), [Rituxan[®] USPI 2021](#)).

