8.2.3. End of Treatment Safety Follow-up Visit

A Safety Follow-up visit should occur 30 days (± 7 days) from the last dose of study treatment or prior to the start of a new anticancer treatment. If the subject starts a new anticancer treatment less than 7 days after the treatment termination visit, only those procedures not conducted at the treatment termination visit should be performed at the Safety Follow-up visit.

Subjects who withdraw consent to treatment may still participate in Safety Follow-up. The following procedures will be performed at the Safety Follow-up visit:

- Complete physical exam including weight and eye-related symptom assessment
- Evaluation of ECOG performance status
- Vital signs
- Review of AEs and concomitant medications
- 12-lead ECG (in triplicate [≥ 1 minute apart])
- Collect blood samples and urine for the following clinical laboratory tests:
 - Hematology
 - Serum chemistry
 - Coagulation
 - Urine pregnancy test (for women of reproductive potential only)
 - Urinalysis

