10.5.1. Adverse Events

Adverse event parameters to be evaluated are the type, incidence, and intensity of AEs; the relationship of AEs to study treatment; and the action taken with respect to study treatment due to AEs.

The verbatim terms used in the eCRF by investigators to identify AEs will be coded using the Medical Dictionary for Regulatory Activities (MedDRA).

The treatment-emergent period is defined as the period of time from the first dose of study treatment, until the earlier of:

- Thirty days following the last dose of ibrutinib/placebo or 30 days following the last dose of rituximab, whichever occurs later

OR

- The start date of a new anticancer therapy.

The Treatment-emergent adverse events (TEAEs) are those events that:

- Are not present prior to the treatment-emergent period and occur during the treatment-emergent period,
- The onset dates are missing, and end dates are during treatment-emergent period,
- Are considered related to study drug by the investigator regardless of the start dates of the events, or
- Are present prior to the treatment-emergent period but worsen in severity during the treatment-emergent period or are subsequently considered related to study drug by the investigator.

All TEAEs will be included in the analysis. For each AE, the number and percentage of subjects who experience at least one occurrence of the given event will be summarized. The number and percent of subjects with TEAEs will be summarized according to intensity (CTCAE, v4.03) and drug relationship, as well as categorized by system organ class and preferred term. Summaries, listings, datasets, or subject narratives may be provided, as appropriate, for those subjects who die, who discontinue treatment due to an AE, or who experience a severe AE or a SAE.

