10.5.2. Clinical Laboratory Tests

Laboratory tests will be summarized separately for hematology and serum chemistry. Local laboratory results will be standardized using the International System SI unit. Selected hematologic and chemistry laboratory parameters are detailed in Section 7. All laboratory values will be graded using the NCI CTCAE v4.03. The worst toxicity grade during the study will be tabulated.

A summary of the shifts in selected laboratory hematology and serum chemistry parameters from baseline to the worst toxicity grade during the study will be provided. The worst toxicity grade during the study will be tabulated.

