- l. Response Evaluation Visits: If study drug (ibrutinib/placebo) is held before a scheduled response assessment, then the response assessment can be delayed up to 2 weeks to allow re initiation of study drug prior to the scheduled response assessment. Subjects who discontinue study treatment for reasons other than progressive disease will participate in ongoing response evaluation assessments as detailed in Section 8.3.1.
- m. End of Treatment Safety Follow Up: 30 ±7 days after last dose of study treatment or prior to subsequent therapy. May occur sooner if subject is scheduled to start a new anticancer treatment.
- n. Randomization should occur as close to the time of the expected first dose as possible and not more than 72 hours prior to the expected first dose of study treatment.
- o. Subjects will be randomized to a study treatment assignment and will continue on this study treatment assignment until study treatment discontinuation as described in the protocol Section 8.
- p. Peripheral blood MRD assessment for subjects terminating study treatment who have not experienced progressive disease.
- q. Once a subject progresses, he/she will be contacted approximately every 24 weeks from the last dose by clinic visit or telephone to assess survival for up to the end of the study. Subsequent anticancer therapies, best response to therapy, and information about other malignancies will be collected.

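### SAP Section 5 stops counting laboratory, vital-sign and eye-symptom values at day 30 after last dose, but the protocol allows the Safety Follow-up visit up to day 37

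*SAP*

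**What the plan says.** SAP Section 5 defines the treatment-emergent period as running from first dose "up to 30 days after the date of the last dose of study treatment or the day before initiation of subsequent anti-cancer therapy", whichever is earlier. It then restricts the safety data: "Unless otherwise specified, only baseline and post-baseline values collected during the treatment-emergent period will be included in the safety analysis". SAP Table 7 lists the summaries this governs: worst post-baseline grade for selected hematology and chemistry tests, abnormalities in creatinine clearance, uric acid and liver function, vital signs, and new or worsened eye symptoms. None has a wider window.

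Protocol 8.2.3 fixes the visit: "A Safety Follow-up visit should occur 30 days (± 7 days) from the last dose of study treatment", or before new anticancer treatment starts. Footnote m of the Schedule of Assessments (Appendix A) agrees: "30 ±7 days after last dose of study treatment or prior to subsequent therapy". The visit includes hematology, serum chemistry, vital signs and an eye-symptom assessment, among other procedures.

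For laboratory data, Protocol 10.5.2 sets no 30-day limit: "The worst toxicity grade during the study will be tabulated". The SAP introduction gives the SAP precedence where methods differ. SAP 8.1, which records changes from the protocol's planned analyses, has three entries, and none concerns this restriction.

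**The concern.** Two windows are counted from the same date, and the analysis window closes inside the visit window. A subject seen on day 29 contributes end-of-treatment values to the tables. A subject seen on day 33, equally on schedule, does not. Inclusion then depends on which permitted day the subject attends and not on what was measured.

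This is the scheduled off-treatment safety assessment, and its values are collected whichever day it falls on. What is at stake is a worst grade or an abnormal vital sign or eye symptom that is first seen at that visit. Adverse-event reporting would not always recover it. Under Protocol 11.4.2, collection also ends 30 days after last dose, apart from serious events considered related. A non-serious laboratory abnormality that begins on day 33 could be absent from both sets of tables.

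**Working it through.** The plan states no figure for this, so the check is a day count and a comparison of the texts.

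**Inputs**
- Visit target 30 days after last dose, tolerance ± 7 days (Protocol 8.2.3; Appendix A, footnote m).
- Last analysable day: 30 days after last dose, absent earlier subsequent therapy (SAP Section 5).
- Anchor: last dose of study treatment in both documents. The SAP introduction defines study treatment as ibrutinib, placebo and/or rituximab. Protocol 10.5.1 takes the later of the two drugs: "Thirty days following the last dose of ibrutinib/placebo or 30 days following the last dose of rituximab, whichever occurs later".

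**Day count**
- Permitted days: 30 − 7 = 23 to 30 + 7 = 37, so 37 − 23 + 1 = 15 days.
- Permitted days after the cut-off: 31 to 37, so 37 − 30 = 7 days.
- Share of permitted days excluded: 7/15 = 46.7%. Share kept: 8/15 = 53.3%.
- With the cut-off at day 37 for these values: 0/15 excluded.

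**From days to subjects.** The documents do not give the distribution of actual visit days. If visits were spread evenly over the window, 47% would fall after day 30. If they centred on day 30 with an SD of 3 days, whole-day rounding gives P(day ≥ 31) = P(Z > 0.5/3) = 0.43. Both spreads are assumptions. The possible range is 0% (all visits by day 30) to 100% (all on days 31 to 37). Visits brought forward because new therapy is starting are less likely to fall late.

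**From subjects to tables.** A worst-grade entry changes only if two things happen together:

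share of subjects changed = P(visit on days 31–37) × P(that visit gives a grade worse than every earlier post-baseline value | visit on days 31–37).

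The documents give no value for the second factor. Earlier draws make it likely to be small. Hematology and chemistry are taken on Cycle 1 Days 8, 15 and 22, on Day 1 of Cycles 2 and 3, and on Day 1 of each odd cycle afterwards. The Treatment Termination visit (Protocol 8.2.2) repeats them, with vital signs and eye symptoms. A subject who stops during Cycle 2 already has four scheduled post-baseline draws (Cycle 1 Days 8, 15 and 22; Cycle 2 Day 1), plus termination tests.

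**Search for a rule that removes the conflict.** The restriction allows for exceptions, but no exception or visit-windowing rule in the SAP covers these measurements. Table 8 of the SAP windows only disease assessments. One column header in Appendix A places the visit within 30 days, but the window row of that table gives ± 7 days and footnote m gives 30 ± 7, so the header does not settle it.

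**The case against.** The strongest defence is consistency. Adverse-event collection, concomitant-medication recording, the protocol's treatment-emergent period and the denominator of the exposure-adjusted incidence rate (EAIR) in SAP 5.1 all end at last dose plus 30 days. A longer window for measured values would differ from the adverse-event window and would add days on which concomitant medication is no longer collected. The safety tables are descriptive, with no formal testing, so type I error and power are untouched. This stands as a reason to keep the 30-day rule for adverse events and to expect a small effect. It does not explain why values from an on-schedule visit should be kept or lost by day of attendance.

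A reader might infer more than the documents support:

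- **That all safety data after day 30 are lost.** SAP Section 5 counts treatment-related events as treatment-emergent whatever their timing. An event that began by day 30 still counts if it is recorded at a later visit. Related serious events are reported after 30 days. The loss concerns measured values.
- **That everything collected at the visit is discarded by this rule.** Coagulation, urinalysis and ECG have no planned summary in Table 7, so the cut-off removes nothing from a table for them.
- **That early stoppers, and so one arm, are affected more.** The laboratory schedule is densest in the early cycles, and termination tests follow whenever treatment stops. No document gives stopping rates or visit timing by arm.
- **That long cytopenias will be missed.** Protocol 1.3.2 says: "The median duration of lymphopenia was 14 days (range, 1-588 days) and of neutropenia was 13 days (range, 2-116 days". These are durations, not onset times. A cytopenia that began on treatment would usually show in earlier draws, and the worst-grade table would already hold it.

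**Conclusion.** The mismatch is real for hematology, chemistry, vital signs and eye symptoms: 7 of 15 permitted visit days fall after the analysis window closes. This conclusion rests only on the stated windows and their common anchor. For laboratory grades it also narrows Protocol 10.5.2 without an entry in SAP 8.1.

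The 47% is a share of permitted days. It is not a share of subjects or of missed toxicities, neither of which the documents allow one to estimate. The expected effect on worst-grade tables is small, on the assumption that most worst grades appear in on-treatment or termination draws. Efficacy results are unaffected, and a difference between arms is not shown. This is a cheap improvement to the plan with a small expected effect.

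**What to change.** Add one sentence to SAP Section 5. For laboratory, vital-sign and eye-symptom summaries, values from the scheduled End of Treatment Safety Follow-up visit are included through day 37 after last dose, or up to the day before subsequent anti-cancer therapy if that is earlier. Leave the 30-day definition of treatment-emergent adverse events and the EAIR denominator as they are. Add an entry to SAP 8.1 stating how the laboratory window differs from Protocol 10.5.2.

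The cost is that sentence, the SAP 8.1 entry and a small programming change. No visit, procedure or clinical rule changes. The downside is up to 7 more off-drug days in descriptive summaries, and a window for measured values that is slightly longer than the one for adverse events; a table footnote can say so.

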**Table 7. Summary of Safety Assessments**

Assessment Type	Definition	Analysis Methods
AE	TEAEs, COVID-19 TEAEs, SAEs, grade 3 or worse TEAEs, related TEAEs, TEAEs leading to treatment discontinuation, TEAEs leading to dose reduction, TEAEs leading to death, protocol- defined events of special interest and other safety observations.	Descriptive summary statistics and/or listings
Lab	Worst post-baseline toxicity grade for selected CTCAE gradable hematology and chemistry. Abnormalities in creatinine clearance, uric acid, and liver function.	Descriptive summary statistics and/or listings
Vital Signs and other Observations Related to Safety	Blood pressure, heart rate, body temperature, new or worsened eye-related symptoms	Descriptive summary statistics and/or listings

TEAE: treatment emergent adverse event; SAE: serious adverse event; CTCAE: Common Terminology Criteria for Adverse Events

### 5.1 Exposure-Adjusted Incidence Rate

Exposure-adjusted incidence rate (EAIR) takes into account the patients' exposure time in quantifying the risk of an AE. For a given AE, EAIR is defined as the rate of the number of patients who experience at least one event over total time at risk for all subjects (Zhou, et. al.

2015; Jia, et. al. 2020). EAIR "adjusts for exposure" by accounting for the variability in patients time at risk as opposed to crude incidence rates, which divides the number of patients with events by the total number of patients. The time at risk is different for patients who have experienced the event and subjects who are event-free throughout the treatment-emergent period.

For patients with at least one event, the time at risk is the time from first dose date to the start date of the first event. The choice to restrict the time at risk to the onset of first event is due to EAIR's epidemiological origin and is based on the assumption that occurrences of multiple events are interdependent. Hence, for patients with events, the time at risk can be represented, in patient-years at risk, as:

$$(Start\ date\ of\ the\ first\ event - first\ dose\ date + 1)/365.25 \quad (equation\ 1)$$

For patients with no event, the time at risk is the time from the first dose date to the end of the treatment-emergent period which can be represented, in patient-years at risk, as:

$$(Last\ dose\ date + 30\ days - first\ dose\ date + 1)/365.25 \quad (equation\ 2)$$

The *total patient-years at risk* is the sum of the patient-years at risk for all subjects. For patients with events, patient-years at risk is calculated using equation 1, while for patients with no event, patient-years at risk is calculated using equation 2.

The *100 patient-years at risk* is the total patient-years at risk divided per 100 patients and can be interpreted as the average of length time (in years) to observe the first onset of AE if 100 patients were treated for 1 year.

For a given AE, the EAIR is represented as the number of patients with events per 100 patient-years at risk:

$$(Number\ of\ subjects\ with\ events/total\ patient-years\ at\ risk)*100,$$

or, equivalently

$$Number\ of\ subjects\ with\ events/100\ patient-years\ at\ risk$$

An equivalent interpretation of EAIR can be expressed as the "average number of patients experiencing the event of interest if 100 patients were treated for 1 year".

EAIRs may be summarized for all TEAEs, fatal TEAEs, and serious TEAEs.

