1.3.2.1. Infusion Reactions

Rituximab can cause severe, including fatal, infusion reactions. Severe reactions typically occurred during the first infusion with time to onset of 30-120 minutes. Rituximab-induced infusion reactions and sequelae include urticaria, hypotension, angioedema, hypoxia, bronchospasm, pulmonary infiltrates, acute respiratory distress syndrome, myocardial infarction, ventricular fibrillation, cardiogenic shock, anaphylactoid events, or death. Premedicate patients with an antihistamine and acetaminophen prior to dosing.

In the majority of patients with NHL, infusion reactions consisting of fever, chills/rigors, nausea, pruritus, angioedema, hypotension, headache, bronchospasm, urticaria, rash, vomiting, myalgia, dizziness, or hypertension occurred during the first rituximab infusion. Infusion reactions typically occurred within 30 to 120 minutes of beginning the first infusion and resolved with slowing or interruption of the rituximab infusion and with supportive care (diphenhydramine, acetaminophen, and intravenous saline). The incidence of infusion reactions was highest during the first infusion (77%) and decreased with each subsequent infusion.

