### 1.3 Sample Size Determination

#### Sample Size Consideration for PFS

A sample size of approximately 440 subjects (actually enrolled 445 subjects) were randomized to Arms A and B to evaluate whether treatment in Arm A will result in a prolongation of progression-free survival (PFS) when compared to Arm B in treatment naïve subjects with follicular lymphoma. The sample size was determined according to the Group Sequential Design with 2 interim analyses. For this calculation, the references used for the assumptions were [Hainsworth 2002](#), [Ghielmini 2004](#), [Zucca 2019](#), and [Fowler 2020](#). Assuming exponential survival distribution for the PFS events and 66.7% improvement in median PFS of Arm A over Arm B (a hazard ratio [HR] of 0.60), the study has approximately 87% power with 200 observed PFS events using an overall 1-sided significance level of 0.025. For the sample size calculation, a median PFS of 28 months in the control arm, and the actual enrollment rates using a 3-month average until November 2020 and a projected enrollment rate of 8 subjects per month afterwards were used. Two interim analyses were planned with the first interim analysis (IA1) for futility and the second interim analysis (IA2) for efficacy.

IA1 was planned when approximately 55% of the 200 PFS events had occurred. The futility boundary was based on a Rho parameter of 5. Following review of the data at IA1, the DMC suggested continuing the study without modification.

IA2 was planned after approximately 75% of the 200 PFS events (ie, 150 PFS events) were observed and after the last subject had been enrolled, and at least 90% of the subjects had had the opportunity to be followed on study for at least 1 year. The 1-sided  $\alpha$  0.025 for PFS was split: 0.001 allocated to PFS IA2 and 0.024 allocated to primary analysis for PFS, following the Bonferroni rule, [Table 3.1](#). Following review of the data at IA2, the DMC suggested continuing the study without modification.

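### SAP 5.1 misdescribes the exposure-adjusted incidence rate as a count of patients, and does not say that it adjusts for unequal exposure only when the event rate is roughly constant

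*SAP*

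**What the plan says.** SAP 5.1 defines the EAIR as "the number of patients who experience at least one event over total time at risk for all subjects", multiplied by 100. For a patient with an event, "the time at risk is the time from first dose date to the start date of the first event" (equation 1). For a patient without one, "the time at risk is the time from the first dose date to the end of the treatment-emergent period", calculated as last dose plus 30 days (equation 2).

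Two sentences then interpret the quantities. One takes total patient-years divided by 100 and reads it as an average length of time to first onset. The other says the EAIR is equivalent to the "average number of patients experiencing the event of interest if 100 patients were treated for 1 year". The section presents the rate as an adjustment for exposure. It states no constant-rate condition and gives no caution for the case where the arms differ in time on treatment.

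The use is limited: "EAIRs may be summarized for all TEAEs, fatal TEAEs, and serious TEAEs". Protocol 10.5 plans no formal testing of safety data. SAP Table 7 keeps the ordinary descriptive TEAE summaries, and SAP 5.2 adds TEAE prevalence by yearly interval of ibrutinib/placebo treatment.

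**The concern.** A rate of first events per 100 patient-years is not a number of patients out of 100. The two are close when the rate is low and diverge as it rises. All TEAEs, the first category named for the EAIR, is where the rate will be highest.

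The second issue is what the rate adjusts for. If risk is concentrated early, patients who remain event-free keep adding years to the denominator after the risk has largely passed. The arm treated for longer adds more of them, so equal early risk produces unequal EAIRs. The conditions for this are present here: study drug continues to progression, SAP 5.2 plans intervals out to more than 6 years, and Protocol 1.3.2.1 documents one early-onset event: "The incidence of infusion reactions was highest during the first infusion (77%) and decreased with each subsequent infusion".

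At stake is how a clinical study report describes toxicity. A reader who takes the SAP's sentence at face value will misstate absolute risk, and may read a lower EAIR in one arm as lower risk when it reflects longer exposure.

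**Working it through.** **Inputs.** The plan gives no EAIR value and no expected treatment duration by arm, so there is no stated figure to reproduce. As a proxy for time on treatment I take the design PFS from SAP 1.3: "a median PFS of 28 months in the control arm" and HR 0.60, giving an Arm A median of 28/0.60 = 46.7 months. These inputs agree with the plan's own power: 200 events, 3:1 allocation, one-sided 0.024 gives Φ(√(200 × 0.75 × 0.25) × ln(1/0.60) − 1.977) = Φ(1.15) = 87.5%, against about 87% stated.

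**1. The patient-count reading under a constant hazard.** With hazard L per year, the EAIR is 100L, but the expected number of patients with the event among 100 treated for one year is 100(1 − e^−L).

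| EAIR | Patients per 100 in one year |
|---|---|
| 5 | 4.9 |
| 10 | 9.5 |
| 20 | 18.1 |
| 50 | 39.3 |
| 100 | 63.2 |
| 200 | 86.5 |

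The reading is adequate up to about 10 per 100 patient-years and poor beyond that.

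**2. All TEAEs.** Mean exposure to the earlier of PD and 60 months is (1 − e^−60λ)/λ with λ = ln 2/median: 3.31 years (A) and 2.60 years (B). Adding 30 days gives 3.39 and 2.69 years. Assume 98% have a TEAE at a mean of 0.05 years:
- A: 98/(0.98 × 0.05 + 0.02 × 3.39) = about 839
- B: 98/(0.98 × 0.05 + 0.02 × 2.69) = about 954

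Neither can be a number of patients out of 100. A separate simulation with 97% affected uniformly over the first month gives about 680 (A) and 800 (B).

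**3. The time-to-onset reading.** Total patient-years divided by 100 is a denominator. Doubling the number of patients with the same event pattern doubles it, while the average time to first onset does not change.

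**4. Where the adjustment works.** With a constant hazard of 0.20 per year and the design exposures, simulated EAIRs are 20.0 in both arms, although crude incidence is 46% (A) and 38% (B).

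**5. Where it does not.** Take equal 30% risk confined to the first month (mean onset 0.04 years), with exposure to PD capped at 5 years:
- A: 30/(0.30 × 0.04 + 0.70 × 3.39) = 12.6
- B: 30/(0.30 × 0.04 + 0.70 × 2.69) = 15.9
- Ratio 0.79 (0.82 with a 4-year cap, 0.77 with 6 years)

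In this example 30 patients in 100 have the event within the year in either arm. On the same inputs, a true early risk of 35% in Arm A gives 35/(0.35 × 0.04 + 0.65 × 3.39) = 15.8, about equal to Arm B's rate at 30%.

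**6. Sensitivity.** Simulation of 1,000,000 patients per arm, onset uniform over months 0 to 3, equal risk of 10%, 30% or 60%. Follow-up of 47 to 77 months comes from the PFS analysis at about 77 months (Protocol 10.3) less 30 months' accrual (Protocol 3.1).

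| Time-on-treatment assumption | EAIR ratio A/B |
|---|---|
| To PD, follow-up 47–77 months | 0.79–0.80 |
| To PD, follow-up 29–77 months | 0.81–0.83 |
| To PD, follow-up 34–84 months | 0.80–0.81 |
| To PD, plus 10%/year other stopping in both arms | 0.81–0.82 |
| To PD, no cut-off | 0.61–0.62 |
| Other stopping 10%/year in A, none in B | 0.97–0.98 |
| Other stopping 15% vs 5%, or 20% vs 10%, per year | 0.99–1.00 |
| No PFS difference | 0.99–1.01 |

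A deficit of 20% needs mean exposure about 1.25 times as long in Arm A. With milder excess stopping in Arm A (0.008 vs 0.003 per month, assumed), the step 5 calculation gives about 0.90.

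**7. Cumulative incidence as an alternative.** With end of treatment as a competing event at rate λ, incidence by time t is L/(L + λ) × (1 − e^−(L+λ)t). For an equal constant L = 0.20 per year, the design λ (0.178 and 0.297 per year), no 30-day tail and t = 4 years, this gives 41.2% (A) and 34.7% (B), a ratio of 1.19. It too depends on treatment duration, in the opposite direction.

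**The case against.** A reader might infer that the EAIR is the plan's main correction for unequal exposure and that it would hide a real excess of early toxicity. The documents do not support that. The EAIR is optional, nothing is tested, and the crude percentages in Table 7 remain. For an event confined to the first weeks, the crude percentage is almost unaffected by later exposure, so an early excess would show there. It should also show in the first-year interval of SAP 5.2, although that table reports prevalence, mixing new and ongoing events. Infusion reactions, the one event whose early onset the protocol documents, have their own analysis as a proportion with a chi-square test (SAP Table 6).

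It is also fair that no EAIR is planned for individual early events. The protocol gives no onset timing for ibrutinib-related cytopenias or diarrhoea, and nothing in either document shows that serious or fatal TEAEs cluster early.

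Finally, the 20% is not a property of the plan. The documents give neither treatment duration by arm nor a rate of stopping for toxicity. An excess of about 10 percentage points per year in Arm A removes the gap.

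All of this stands, and it limits the importance of the point. It does not rescue the two interpretation sentences, which are wrong whatever the exposure turns out to be, and it does not supply the missing constant-rate condition.

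**Conclusion.** Both interpretation sentences in SAP 5.1 are incorrect. The patient-count sentence overstates by about a quarter at an EAIR of 50 (50 against 39) and by more than half at 100 (100 against 63), under the constant hazard most favourable to it. For all TEAEs it can yield an impossible number; the 839 and 954 above rest on an assumed 98% affected at a mean of 0.05 years.

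The EAIR's claim to adjust for exposure holds only for a roughly constant first-event hazard. With early onset and equal true risk, it is lower in whichever arm is treated longer. The deficit is about 20% if time on treatment follows a 28-month control median and HR 0.60 with equal other stopping, and ranges from none to 39% across the assumptions tried. It would be too strong to say that ibrutinib's rate will be diluted by 20%: which arm stays on treatment longer is not stated, and depends on toxicity stopping as well as PFS.

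Because the table is optional and descriptive, and other planned summaries would show an early excess, this is a matter to consider. It does not threaten the safety analysis.

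**What to change.** In SAP 5.1, delete both interpretation sentences. Describe the EAIR as a rate of first events per 100 patient-years that summarises risk across unequal exposure only if that rate is roughly constant over time.

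Wherever EAIRs are reported (all, serious and fatal TEAEs), also give them by period since first dose, for example 0–6, >6–24 and >24 months. Say that they are to be read beside the crude incidence and the yearly summaries of section 5.2.

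Cumulative incidence with end of treatment as a competing event could be added as a supplement. It should not replace the EAIR, because it has its own dependence on treatment duration (step 7 of the working).

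The cost is a wording change and one extra descriptive table from dose and onset dates that the EAIR already uses, with fewer events per cell. No efficacy analysis or alpha allocation is affected.
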